## FUNDING/SUPPORT

0 unresolved  
comment(s)

If the research is being submitted to, supported by, or conducted in cooperation with an external or internal agency or funding program, indicate below all the categories that apply. [?](#)

 Not applicable

## Check All That Apply

- Grant application pending
- (HHS) Dept. of Health & Human Services
  - (NIH) National Institutes of Health
  - (CDC) Centers for Disease Control & Prevention
  - (HRSA) Health Resources and Services Administration
    - (SAMHSA) Substance Abuse and Mental Health Services Administration
  - (DoJ) Department of Justice or Bureau of Prisons
  - (DoE) Department of Energy
  - (EPA) Environmental Protection Agency
  - Federal Agencies Other Than Those Listed Here
  - Industry (Other than Pharmaceutical Companies)
  - Internal Grant Program w/ proposal
  - Internal Grant Program w/o proposal
  - National Science Foundation
  - Other Institutions of Higher Education
  - Pharmaceutical Company
  - Private Foundation/Association
  - U.S. Department of Education
  - State

Other:

Specify the funding source and/or cooperating organization(s) (e.g., National Cancer Institute, Ford Foundation, Eli Lilly & Company, South Western Oncology Group, Bureau of Prisons, etc.):

Click applicable listing(s) for additional requirements and information:

- [\(HHS\) Dept. of Health & Human Services](#)
- [\(NIH\) National Institutes of Health](#)
- [\(CDC\) Centers for Disease Control & Prevention](#)
- [\(HRSA\) Health Resources & Services Administration](#)
- [\(SAMHSA\) Substance Abuse & Mental Health Services Administration](#)
- Industry (Other than Pharmaceutical Companies) [[IRB Fee Info](#)]
- [National Science Foundation](#)
- [\(DoEd\) U.S. Department of Education](#)
- [\(DoJ\) Department of Justice or Bureau of Prisons](#)
- [\(DoE\) Department of Energy Summary](#) and [Department of Energy Identifiable Information Compliance Checklist](#)
- [\(EPA\) Environmental Protection Agency](#)

## Add Related Grants

If applicable, please search for and select the OSPA Account number or Electronic Internal Approval Form (eIAF) # (notif #) associated with this IRB application using the "Add Related Grants" button.

If required by your funding agency, upload your grant using the "Grant/Contract Attachments" button.

The research involves use of Department of Defense (DoD) funding, military personnel, DoD facilities, or other DoD resources. (See [DoD SOP](#) and [DoD Summary](#) for details)

 Yes  No

Using the "attachments" button (below), attach applicable materials addressing the specific processes described in the DoD SOP.

Additional Certification: (If your project is federally funded, your funding agency may request an Assurance/ Certification/Declaration or Exemption form.) Check the following if needed:

Protection of Human Subjects Assurance/Certification/Declaration of Exemption (Formerly Optional Form – 310)

Assurance/Certification Attachments

## OTHER REVIEW COMMITTEES

0 unresolved  
comment(s)

If you check any of the below committees, additional materials may be required with your application submission.

Does your research fall under the purview of any of the other review committees listed below? [If yes, check all that apply and attach applicable materials using the attachment button at the bottom of your screen.]

Yes  No

Additional Information	
 Institutional Biosafety Committee	

• Institutional Biosafety Committee (IBC) - Attach required IBC materials

 Radiation Safety Committee	

• Radiation Safety Committee (RSC) - For applicability, see instructions and attach form

 Radioactive Drug Research Committee	

• Radioactive Drug Research Committee (RDRC)

 Markey Cancer Center (MCC) Protocol Review and Monitoring Committee (PRMC)	

• Markey Cancer Center (MCC) Protocol Review and Monitoring Committee (PRMC)** - Attach MCC PRMC materials, if any, per instructions.

 Graduate Medical Education Committee (GME)	

• Office of Medical Education (OME)

 Office of Medical Education (OME)	

• Graduate Medical Education Committee (GME)

**Attachments**

**\*\* If your study involves cancer research, be sure to select "Cancer Research" in the "Research Attributes" section.** ORI will send your research protocol to the Markey Cancer Center (MCC) Protocol Review and Monitoring Committee (PRMC). The [MCC PRMC](#) is responsible for determining whether the study meets the National Cancer Institute (NCI) definition of a clinical trial and for issuing documentation to you (the investigator) which confirms either that PRMC approval has been obtained or that PRMC review is not required. Your IRB application will be processed and reviewed independently from the PRMC review.

## ADDITIONAL INFORMATION/MATERIALS

0 unresolved  
comment(s)

Do you want specific information inserted into your approval letter?  Yes  No

## Approval Letter Details:

If you wish to have specific language included in your approval letter (e.g., serial #, internal tracking identifier, etc...), type that language in the box below exactly as it should appear in the letter. The text you enter will automatically appear at the top of all approval letters, identical to how you typed it, until you update it. Don't include instructions or questions to ORI staff as those will appear in your approval letter. **If these details need to be changed for any reason, you are responsible for updating the content of this field.**

## Additional Materials:

If you have other materials you would like to include for the IRB's consideration, check all that apply and attach the corresponding documents using the Attachments button below.

- Detailed protocol
- Dept. of Health & Human Services (DHHS) approved protocol (such as NIH sponsored Cooperative Group Clinical Trial)
- Other Documents

Protocol/Other Attachments

NOTE: [Instructions for Dept. of Health & Human Services \(DHHS\)-approved protocol](#)

If you have password protected documents, that feature should be disabled prior to uploading to ensure access for IRB review.

To view the materials currently attached to your application, click "All Attachments" on the left menu bar.

## SUBMISSION INFORMATION

0 unresolved  
comment(s)

\*\*\* If this Continuation Review entails a change in the scope of your activities to include COVID-19 related research, please insert "COVID19" at the start of your Project and Short Titles.\*\*\*

Each Section/Subsection in the menu on the left must have a checkmark beside it (except this Submission section) indicating the Section/Subsection has been completed. Otherwise your submission for IRB review and approval cannot be sent to the Office of Research Integrity/IRB.

If applicable, remember to update the Approval Letter Details text box under the Additional Information section

If your materials require review at a convened IRB meeting which you will be asked to attend, it will be scheduled on the next available agenda and you will receive a message to notify you of the date.

If you are making a change to an attachment, you need to delete the attachment, upload a highlighted version that contains the changes (use Document Type of "Highlighted Changes"), and a version that contains the changes without any highlights (use the appropriate Document Type for the item(s)). Do **not** delete approved attachments that are still in use.

DataCollection	TMS Side effects.doc	TMS Side effects Scale	0.048	gra252	4/5/2023 11:33:11 AM
ResearchProcedures	Penn_Alcohol_Craving_Scale_171.pdf	Alcohol Craving Scale	0.032	gra252	4/5/2023 11:24:54 AM
ResearchProcedures	AUDIT_C.pdf	AUDIT	0.168	gra252	4/5/2023 11:24:38 AM
OtherDeviceDocumentation	StudyDevice_266761.pdf	TMS device description	0.262	gra252	3/28/2023 12:13:05 PM

## Protocol Changes

Click link to sort [Changed Date](#)

HIPAA HIPAAIdentificationCertForm changed by ngmean2 on 3/19/2025 1:17:49 PM

N

Informed Consent ElectronicConsent changed by ngmean2 on 3/19/2025 1:16:42 PM

N

Research Attributes ClinicalResearch changed by ngmean2 on 3/19/2025 1:20:58 PM

Y

Research Attributes ClinicalTrial changed by ngmean2 on 3/19/2025 1:23:17 PM

Y

Research Attributes ClinicalTrial changed by ngmean2 on 3/19/2025 1:23:17 PM

Y

Research Attributes ClinicalTrial changed by ngmean2 on 3/19/2025 1:20:58 PM

Y

Research Attributes EpidemiologicBehavioralStudies changed by ngmean2 on 3/19/2025 1:20:58 PM

N

Research Attributes MaterialOfHumanOrigin changed by ngmean2 on 3/19/2025 1:20:58 PM

N

Research Attributes OutcomesHealthServicesResearch changed by ngmean2 on 3/19/2025 1:20:58 PM

N

Research Attributes PatientOrientedResearch changed by ngmean2 on 3/19/2025 1:20:58 PM

Y

Research Sites MultisiteLeadInvestigator changed by ngmean2 on 3/19/2025 1:18:00 PM

N

## Study Personnel Changes:

86853  
CLOSED

No comments

### Statistical analysis plan

We will calculate the mean and standard deviation values for PACS scores and alcohol cue attentional bias values for two time points (baseline and following the second session). This will be done across both cTBS and sham cTBS sessions. We will compare changes in these outcome measures across cTBS and sham cTBS sessions using t-tests.

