**Background**

Include a brief review of existing literature in the area of your research. You should identify gaps in knowledge that should be addressed and explain how your research will address those gaps or contribute to existing knowledge in this area. For interventional research, search PubMed and ClinicalTrials.gov for duplicative ongoing and completed trials with same condition and intervention(s).

Alcohol use disorder (AUD) imposes significant financial burden on society globally and nationally. Alcohol use disorder is the leading risk factor for attributable burden of disease among people ages 25 to 49, the second-leading risk factor among ages 10 to 24, and the ninth-leading risk factor among all ages (1). Although pharmacotherapy and behavioral treatments have been approved for AUD, their effects sizes are modest (2). Noninvasive neuromodulation can offer an alternative treatment option for AUD (3). Transcranial magnetic stimulation (TMS) is a method of noninvasive neuromodulation that utilizes a magnetic field to focal electrical current in the brain (4). When these electrical currents are focused on specific brain regions, pertinent to the neurobiology of AUD it leads to modulation of behavior and plausibly decrease in alcohol craving and use (5).

Previous TMS studies have used heterogenous parameters, including frequencies ranging from 1 Hz to 20 Hz (3, 6-9). Regions targeted by these studies encompassed ventromedial prefrontal cortex, left dorsolateral prefrontal cortex (left dlPFC) and right dorsolateral prefrontal cortex (3). Two studies used a TMS paradigm with greater efficiency than other routine TMS paradigms, called continuous theta burst stimulation (6, 7). These studies delivered 3600 pulses of cTBS to the left frontal pole/ventromedial prefrontal cortex and showed significant reduction in alcohol cue reactivity and corroborative changes in both resting state and task based functional connectivity (6, 7). Of these two studies, one was notable in comparing active cTBS (3600 pulses per session, one session every day for ten days over two weeks) versus sham cTBS. This study showed that real cTBS led to a significantly greater reduction in brain reactivity to alcohol cues, specifically a reduction in MPFC-striatum and MPFC-insula connectivity 2 and 3 months after TBS treatment (6).

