## Objectives

List your research objectives. Please include a summary of intended research objectives in the box below.

To demonstrate whether two sessions of continuous TBS (cTBS) decreases attentional bias for alcohol cues, alcohol craving and changes resting state functional connectivity in people with alcohol use disorder (AUD) compared to two sessions of sham cTBS. We hypothesize 2 sessions of cTBS to the left dorsolateral prefrontal cortex (L. dlPFC) will significantly decrease attentional bias for alcohol cues, alcohol craving and change resting state functional connectivity in a population of people with AUD compared to sham cTBS.

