## Study Design

Describe and explain the study design (e.g., observational, secondary analysis, single/double blind, parallel, crossover, deception, etc.).

- **Clinical Research:** Indicate whether subjects will be randomized and whether subjects will receive any placebo.
- **Community-Based Participatory Research:** If you are conducting [community-based participatory research \(CBPR\)](#), describe strategies for involvement of community members in the design and implementation of the study, and dissemination of results from the study.
- **Qualitative research:** Indicate ranges where flexibility is needed, if a fixed interview transcript is not available, describe interview topics including the most sensitive potential questions.
- **Research Repositories:** If the purpose of this submission is to establish a Research Repository (bank, registry) and the material you plan to collect is already available from a commercial supplier, clinical lab, or established IRB approved research repository, provide scientific justification for establishing an additional repository collecting duplicate material. Describe the repository design and operating procedures. For relevant information to include, see the [UK Research Biospecimen Bank Guidance](#) or the [UK Research Registry Guidance](#).

This will be a within participant single blinded trial. Recruitment for the study will be done by research assistant and/or principal investigator. All study participants will receive active cTBS first and sham cTBS stimulation one week later. Although participants will be blinded to the intervention, the PI ([name]) and his research assistant will not be blind to the intervention and will deliver the sessions. We will recruit 30 subjects who will receive both active and sham cTBS.

On day one of the study, we will perform baseline assessments including breath alcohol level, alcohol attentional bias tasks using eye tracker, and collection of baseline demographics. All of these baseline assessments will take a total of three hours. We will also obtain resting and active motor threshold from the first dorsal interosseous (FDI) muscle. Following this subjects will be transported to Magnetic Resonance Imaging and Spectroscopy Center (MRISC), affiliated with University of Kentucky for collection of their baseline MRI brain scan that will last thirty minutes. A study team member will escort them to the MRISC and will be with them when the scan is obtained.

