On day two of the study all study participants will receive active stimulation which is two sessions of continuous theta burst stimulation (cTBS) to the left dorsolateral prefrontal cortex. Both sessions will be separated by 50 minutes. Participants will perform the alcohol craving scale, AUDIT-C and attentional bias for alcohol cues before and after the two cTBS sessions. The same sequence of events will occur on day three of the study, but all participants will receive sham cTBS. We will acquire functional MRI (fMRI) scan on both study days 2 and 3, after the active cTBS sessions and sham cTBS session respectively. Study days 2 and 3 will be separated by a week.

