**Research Procedures**

Describe how the research will be conducted.

- What experience will study participants have?
- What will study participants be expected to do?
- How long will the study last?
- Outline the schedule and timing of study procedures.
- Provide visit-by-visit listing of all procedures that will take place.
- Identify all procedures that will be carried out with each group of participants.
- Describe deception and debrief procedures if deception is involved.

Differentiate between procedures that involve standard/routine clinical care and those that will be performed specifically for this research project. List medications that are explicitly forbidden or permitted during study participation.

On day one of the study, following informed consent, we will perform baseline assessments including breath alcohol level, alcohol craving questionnaire, alcohol attentional bias tasks using eye tracker, and collection of baseline demographics. All of these baseline assessments will take a total of three hours. We will evaluate for any contraindications for MRI using the MRI checklist (attached). We will also obtain resting and active motor threshold from the first dorsal interosseous (FDI) muscle. Following this subjects will be transported to Magnetic Resonance Imaging and Spectroscopy Center (MRISC), affiliated with University of Kentucky for collection of their baseline MRI brain scan that will last thirty minutes. A study team member will escort them to the MRISC and will be with them when the scan is obtained.

On the second day, subjects will receive two sessions of active cTBS. Sessions will be the same in dosing and will be delivered at an interval of fifty minutes. Each session will last five minutes regardless of it being cTBS or sham cTBS. Active cTBS sessions will be delivered 120% resting motor threshold (RMT) to the left dorsolateral prefrontal cortex using a figure 8 coil and MagVenture MagPro x100 device (MagVenture A/S, Denmark), with TMS coil position stabilized using BrainSight (Rogue Solutions, Montreal, Canada). Subjects will also perform a host of other tasks as shown in figure 1 before and after the two cTBS sessions. At the end of the cTBS sessions and tasks, post session MRI brain scan will be collected at MRISC.

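### Does leaving baseline undefined in the SAP let a Day 1 score be used that would hide a lasting active effect?

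*Combined protocol and SAP*

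**What the plan says.** The whole analysis plan is one short paragraph. It will give means and standard deviations for "PACS scores and alcohol cue attentional bias values for two time points (baseline and following the second session", for the active and the sham condition alike, and then: "We will compare changes in these outcome measures across cTBS and sham cTBS sessions using t-tests". It covers craving (PACS) and attentional bias only. It does not say on which day the baseline was measured, or whether the t-tests are paired.

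The protocol offers up to three candidate scores per outcome.

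- Day 1. Research Procedures lists "baseline assessments including breath alcohol level, alcohol craving questionnaire, alcohol attentional bias tasks using eye tracker". Study Design lists the attentional-bias task on Day 1 but not craving, and adds "collection of their baseline MRI brain scan that will last thirty minutes".
- Day 2, before active stimulation. Study Design has participants complete the craving scale, AUDIT-C and "attentional bias for alcohol cues before and after the two cTBS sessions".
- Day 3, before sham. Study Design repeats the Day 2 sequence, with sham in place of active.

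The order is fixed: active on Day 2, sham one week later. Imaging after Day 1 consists of a "functional MRI (fMRI) scan on both study days 2 and 3, after the active cTBS sessions and sham cTBS session respectively", with no pre-session scan listed.

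**The concern.** Every dated use of *baseline* in the protocol refers to Day 1; the eligibility criterion on attentional bias uses the word with no day attached. The pre-session scores on Days 2 and 3 are never called baseline. The imaging schedule, with one scan on Day 1 and one after each stimulation day, also fits a single shared baseline. A literal reader could therefore subtract the Day 1 score in both conditions.

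That would matter. The hypothesis is that active stimulation "will significantly decrease attentional bias for alcohol cues, alcohol craving and change resting state functional connectivity". A shared baseline drops out of the active-sham contrast, so an effect lasting a week would lower the sham-day score as well and be counted against active. The protocol's Background makes persistence conceivable: it cites "specifically a reduction in MPFC-striatum and MPFC-insula connectivity 2 and 3 months after TBS treatment". Any unrelated drift between Days 2 and 3 would also enter in full. Only data analysis remains, so an undefined baseline also looks like a choice left open until the results can be seen.

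**Working it through.** **Inputs from the documents.** Planned number 30 (Study Design); 8 enrolled (Subject Info To-Date); fixed order with a one-week gap (Study Design). The documents give no SD, correlation, effect size, significance level or power, so there is no figure to reproduce.

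**Assumed inputs.** Two-sided paired t-test at 5%. The unit is the SD of the Day 2 minus Day 3 post-session difference. r is the correlation between the between-day differences in pre-session and post-session scores. c is the fraction of the active effect δ still present on Day 3, and p is any other Day 3 shift.

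**Step 1, algebra.** A Day 1 baseline (D1) gives

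(post2 − D1) − (post3 − D1) = post2 − post3, with expectation δ(1 − c) − p.

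A same-day baseline gives

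(post2 − pre2) − (post3 − pre3), with expectation δ if the lasting effect and the shift are equal before and after sham.

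With δ = −1 and p = 0, the Day 1 contrast is −1.00, −0.75, −0.50, −0.25 and 0.00 at c = 0, 0.25, 0.5, 0.75 and 1. The same-day contrast is −1.00 throughout. With c = 0 and p = −0.5 or +0.5, the Day 1 contrast is −0.50 or −1.50, so a drift can move it either way.

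**Step 2, precision.** The same-day contrast has SD √(2(1 − r)) in the same unit: 1.41 at r = 0 and 1.00 at r = 0.5.

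**Step 3, chance of a significant result favouring active** (noncentral t, n − 1 degrees of freedom, noncentrality = mean/SD × √n). The same-day columns assume that whatever lasts is equal before and after sham.

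| n, δ | Day 1: c = 0 | c = 0.5 | c = 1 | Same-day: r = 0 | r = 0.2 | r = 0.5 | r = 0.7 |
|---|---|---|---|---|---|---|---|
| 8, 1.0 | 68% | 23% | 2.5% | 41% | 49% | 68% | 88% |
| 8, 0.5 | 23% | 9% | 2.5% | 14% | 16% | 23% | 35% |
| 30, 0.5 | 75% | 26% | 2.5% | 47% | 55% | 75% | 93% |

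The two are equal at c = 1 − 1/√(2(1 − r)): 0.29 at r = 0, 0.21 at r = 0.2 and 0 at r = 0.5. Neither baseline is better in every case.

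**Step 4, which reading the text supports.**

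| Feature of the documents | Same-day baseline | Shared Day 1 baseline |
|---|---|---|
| SAP: two time points, in both conditions | Before and after, on each day: fits | Three distinct scores per outcome over the study |
| SAP: compare changes | Each change carries information | The change reduces to a comparison of post-session scores |
| Study Design: measures before and after stimulation on Days 2 and 3 | All used | Both pre-session measures unused |
| Study Design: Day 1 list | Craving not needed | Craving needed but not listed there |

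The imaging schedule does not tip the balance, because the SAP has no imaging analysis. The comparison of conditions is within participant, so the t-test is naturally a paired one.

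**The case for a change.** The strongest reply is that both readings can be defended, that they estimate different quantities, and that one added sentence would settle the matter at no cost. With 8 people enrolled, the investigator unblinded by design, and a fall in craving already noted in the continuation review, a choice made after seeing results is not a fanciful worry.

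Part of this stands. The definition is absent, the literal use of the word does point to Day 1, and the cancellation is exact. A report should say which score was subtracted, as any report of change scores would.

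The rest is weaker. The harm needs an analyst to adopt the less natural reading, to discard both pre-session measurements, and also needs the effect to persist for a week. The support for persistence concerns connectivity, not craving or gaze, after ten sessions at another target; here there are two sessions on one day. Nor is the same-day version free of cost or risk. It loses power when r is below 0.5 and little persists (41% against 68% at n = 8, δ = 1.0, r = 0). It is also biased if the Day 3 shift differs before and after sham: a difference of 0.3 SD favouring active, with no true effect, gives false claims for active in 11% (r = 0.5) or 16% (r = 0.7) at n = 8, against a nominal 2.5%.

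**Conclusion.** The concern does not call for a change. It identifies a real omission, but the SAP's request for two time points per condition, together with the before-and-after schedule on Days 2 and 3, already leads to the within-person comparison of same-day changes. A definition would write down what an analyst would sensibly do.

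The loss under a Day 1 baseline (68% to 23% to 2.5% at n = 8, δ = 1.0) is conditional on that reading and on assumed persistence, and the documents give no figure for persistence or for r. Comparing the Day 2 and Day 3 pre-session scores as an extra check would alter no result: at n = 8 its 95% interval has half-width 2.365/√8 = 0.84 SD of the difference, too wide to exclude a material shift. Because active always precedes sham, no baseline separates treatment from period. That limitation belongs to the design and is untouched by this point.
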